### 6.3. Termination date

| Data file, identifier
patient_display_id_full | Variable
name | Variable
label         | Variable
level | Nominal
values |
|--|------------------|---------------------------|-------------------|-------------------|
| termination                                      | DSTRDT           | Date of study termination | date              | n.a.              |

## 7. Analysis Sets

### 7.1. Full Analysis Set

| Full Analysis Set |  |  |  |  |  |
|-------------------|--|--|--|--|--|
|                   |  |  |  |  |  |

| Data file, identifier patient_display_id_full | Variable name | Variable label  | Variable Level | Nominal values | Notes |
|---|---------------|---|----------------|----------------|-------|
| enrollment                                    | DMSUBSPS      | Patient signed the informed consent personally  | Nominal        | Yes
No      |       |
| enrollment                                    | DMRPRSPS      | An independent witness signed the informed consent since the patient is unable to write | Nominal        | Yes
No      |       |
| dataSAR                                       | full_set_sar  | All patients  | Nominal        | Yes
No      |       |

| Full Analysis Set |  |  |  |  |  |
|-------------------|--|--|--|--|--|
|                   |  |  |  |  |  |

## 8. Data for a CONSORT diagram and “study realization”

The following data shall be reported:

- Number of patients with enrollment data
- Number of enrollments per site
- Date of FPI, LPI, LPO per site and total
- Cumulative and mean/median FU duration from insertion to last available CRF information
- Cumulative and mean/median FU duration from enrollment to termination date on termination CRF

The following variables will be calculated:

| Data file, identifier patient_display_id_full | Variable name | Variable label    | Variable Level | Nominal values |
|---|---------------|-------------------|----------------|----------------|
| insertion                                     | PRIMSTDT      | Date of insertion | date           | n.a.           |

|                     |                                 |   |       |      |
|---------------------|---------------------------------|---|-------|------|
| enrollment          | dmicdt                          | Date of informed consent                              | date  | n.a. |
| Follow-up_1st       | svstdt -> svstdt_fu1            | Date of visit 1. FU                                   | date  | n.a. |
| Follow-up_3months   | svstdt -> svstdt_fu3m           | Date of visit 3 months FU                             | date  | n.a. |
| Follow-up_12months  | svstdt -> svstdt_fu12m          | Date of visit 12 months FU                            | date  | n.a. |
| hospitalization_log | hostdt                          | Hospitalization Start date                            | date  | n.a. |
| data_sar            | sar_hospstdt_first  | onset date of first hosp.                             | date  | n.a. |
| data_sar            | sar_hospndt_last    | date of resolution/death of last AE                   | date  | n.a. |
| adverse_event       | aestdt                          | Onset Date of AE                                      | date  | n.a. |
| data_sar            | sar_aestdt_first    | onset date of first AE                                | date  | n.a. |
| data_sar            | sar_aeendt_last     | date of resolution/death of last AE                   | date  | n.a. |
| termination         | dstrdt                          | Date of study termination                             | date  | n.a. |
| data_SAR            | sar_last_crf        | Date of last CRF information                          | date  | n.a. |
|                     |                                 |   |       |      |
| data_SAR            | sar_time_crf        | time [days] from insertion to last CRF                | scale |      |
| data_SAR            | sar_time_term       | time [days] from insertion to termination             | scale |      |
| data_SAR            | sar_time_max        | time [days] from insertion to termination or last CRF | scale |      |

For all patients with premature study duration or missing insertion or any violation of in-/exclusion criteria the following variables shall be listed:

- All in-/exclusion criteria
- Date of enrollment
- Date and reason of premature study termination
- Date and type of all other available CRFs (except for AE-CRFs)

## **9. General data**

### **9.1. Analysis set**

All analyses are performed for the full analysis set.

### **9.2. Variables**

[REDACTED]

### **9.3. Treatment of Missing and Spurious Data**

See general definitions in chapter 5.4

### **9.4. Exclusion of Particular Information**

See general definitions in chapter 5.5

No data are excluded from the analysis from the above analysis set and variables.

### **9.5. Descriptive Analyses**

See general definitions in chapter 5.1 and exceptions for reporting numbers and text below the variable tables, if appropriate.

### **9.6. Hypotheses & Statistical Tests**

There are no pre-defined statistical hypotheses.

## 10. Primary Endpoint1

### CIP chapter 7.2.1 - Primary endpoint and hypothesis

SADE-free rate until the 3-month follow-up

A primary endpoint is an SADE (see definition in section 18) that is possibly, probably or causally related to the BIOMONITOR III, the Incision Tool or the Insertion Tool, or the insertion procedure, which occurs before the 3-month follow-up.

SADEs will be adjudicated by an internal adjudication board, whereby the seriousness and device relatedness will be re-examined. If any amply documented external physical influence (e.g. accident, sport) or medical AE caused the SADE, it does not contribute to this endpoint. SADEs that occur later than the 3-month follow-up, and SADEs with onset date later than 105 days after insertion procedure (3 months defined as 91 days after implantation + 14 days would still be in accordance to the CIP) in case the 3-month follow-up was not conducted or conducted outside the specified time interval, do not contribute to this endpoint.

The parameter of interest is the SADE free rate, which will be calculated by

$$\frac{\text{Number of patients with one or more primary endpoint until the 3 months FU}}{\text{Number of patients at the 3 months FU or with primary endpoint}}$$

$$\text{in percent. The period of observation starts with the insertion of the BIOMONITOR III and takes until the 3-month follow-up.}$$

### 10.1. Analysis set

The number of patients with at least one primary endpoint until the 3 months FU (the numerator) will be determined by assessing the variable "AERELPET" in the "AE evaluation" form. This form is filled by the AE evaluation board and the variable "AERELPET" is set to "Yes" if and only if all conditions defined in 7.2.1 in the CIP are met.

The denominator will be calculated as follows:

1. The number of patients with 3 months FU will be counted by the number of non-missing entries in SVSTDT in the "3 month FU" form.
2. The number of patients with primary endpoint will be calculated as defined above.
3. In case of patients lying in the intersection of both sets, these patients will be counted once.
4. Patients without SADE and termination date less than 77 days after insertion will be disregarded.

Patients who do not attend the 3 months FU, but who have not terminated study participation earlier than 77 days after insertion will be included in the analysis.

For the calculation of the Kaplan-Meier analysis, the following time variables will be used:

1. For patients with at least one primary endpoint: time from insertion to time of first primary endpoint [REDACTED]
2. For patients without primary endpoint: time from insertion to last information available [REDACTED]

For the KM analysis data of all patients is used.

## 10.2. Variables

| Data file, identifier patient_display_id_full | Notes   | Variable name                    | Variable label                                 | Variable level | Nominal values |
|---|---|----------------------------------|--|----------------|----------------|
| AE evaluation                                 | sorted by patient_display_id_full and AESTDT and removed duplicates | AERELPET                         | Adverse event is relevant for primary endpoint | nominal        | Yes
No      |
| 3-month FU                                    |   | SVSTDT                           | Date of visit                                  | date           |                |
| 3-month FU                                    |   | sar_3mFU_available  | 3m FU available?                               | nominal        | Yes
No      |
| Termination                                   |   | sar_term_77         | Termination less than 77 days after insertion? | nominal        | Yes
No      |

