18.8 Reporting responsibilities

18.8.1 Reporting responsibilities of the investigator to sponsor

The investigator shall document all events on the respective eCRF pages provided within the CDMS. The indicated timelines for reporting of initial cases and possible update reports shall be strictly followed (see section 18.9).

All AEs and ADEs) shall be reported together with an assessment by completing the AE-CRF in accordance with ISO 14155:2011.

For device deficiencies of the investigational device, a DD-CRF shall be completed.

The reports shall be done with all information available, even if this results in an incomplete report. The investigator has to follow-up ongoing Events either as long as the patient participates in the study, the clinical investigation is terminated prematurely or until the event has been resolved, whatever comes first. Ongoing SADEs related to the investigational device will be followed for a maximum time period of either 4 weeks after pre-mature or regular study termination of the individual patient. This also applies to Adverse Events involving the explantation or replacement of an investigational device, heart transplantation or implantation of a ventricular assist device. This follow-up period is reduced if 'Last Patient Out' is announced in the study. All follow-ups on open adverse events will stop at this point in time at the latest.

Multiple events may occur simultaneously in one subject. For each medically independent event an individual report must be provided.

In addition, the action taken/treatment should also be provided with any supportive documentation available.

The investigator has to ensure that all relevant information is available. This also includes information from other parties (family, other hospitals etc.).

If a patient dies during the study this might be subject to special reporting requirements in some countries. Therefore as much information as possible should be provided to enable BIOTRONIK to explain the circumstances leading to death. At least a pseudomized copy of the death records and an autopsy report (if performed) should be sent to BIOTRONIK promptly. All actions taken, which were initiated to gain further information must be documented in writing and provided to BIOTRONIK.

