#### *CIP chapter 7.1 Objectives*

*This study is designed as a post-market clinical follow-up study to identify and evaluate residual risks associated with the use of the BIOMONITOR III system that are discovered or remain even after risk analysis, risk mitigation and successful conformity assessment. The results will be used to update the clinical evaluation. Furthermore, the study will also provide additional data as required by regulatory authorities outside of the CE-region.*

The main aspects and the design of the clinical investigation are presented in chapters 0-4.

General statistical procedures are summarized in chapter 5. Those methods are used in case there is no other instruction within this document.

Definitions of the specific dates, e.g. effective randomization and termination are presented in chapter 6.

Specific analysis sets are defined in chapter 0.

Descriptive and inferential statistical analyses are handled in following chapters.

Thereby the following statistical considerations are specified:

- Definition of the analysis set for the following analyses, e.g. excluding patients without any measured or imputed data for this endpoint.
- Definition of the endpoint(s) to be analyzed including references to the source data, e.g. CRF sheet and item.
- Treatment of missing and spurious data for evaluation of the above endpoint(s).
- Exclusion of particular information from the evaluation of the above endpoint(s) in addition to the exclusion of patients from the analysis set.
- Descriptive analyses including tables and figures
- Statistical alternative hypothesis/hypotheses (HA) to analyze the above endpoint(s) if available.
- Statistical tests intended to analyze the above hypothesis/hypotheses if available.

All variables are defined in tables using the following columns:

- Data file Name of a data file exported from the CDMS with one data row per unique identifier (e.g. patient specific "patient\_display\_ID\_full") additionally, a new data file ("data\_SAR") is generated by merging all relevant data from the original CDMS data files and generating derived variables (e.g. BMI from weight and height or date of first AE episode)
- Descriptive Information whether data has to be presented with descriptive methods as defined in the following sub-chapter ("Yes") or data needed for generating of derived variables only ("No")

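### SAP 10.2 removes duplicates from the AE evaluation file without first keeping the AERELPET = Yes rows, so an endpoint patient can be lost from the primary count

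*SAP*

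**What the plan says.** SAP 10.1 sets the counting rule: "The number of patients with at least one primary endpoint until the 3 months FU (the numerator) will be determined by assessing the variable" AERELPET, which the AE evaluation board completes. The variable is labelled "Adverse event is relevant for primary endpoint" and takes the values Yes and No, so it describes an event and not a patient.

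SAP 10.2 gives one processing note for it: "sorted by patient_display_id_full and AESTDT and removed duplicates". The same note stands beside the same variable in SAP 14.2 (secondary endpoint 4). Neither AERELPET row carries a footnote mark, although the derived variables in the SAP 10.2 table do.

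Two other places bear on how the note is read. SAP 1.2 describes each data file as exported "with one data row per unique identifier". Protocol 18.8.1 says: "Multiple events may occur simultaneously in one subject", and "For each medically independent event an individual report must be provided".

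**The concern.** The note leaves three things open: whether No rows are removed first, what makes two rows duplicates, and which row survives. Sorting by onset date before removing duplicates most naturally serves to keep each patient's earliest row. Without a filter, that row is the patient's first evaluated event, whatever its flag. A patient with a minor AE in week 1 and an endpoint SADE in week 5 would then be read as having no endpoint.

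That contradicts the numerator in SAP 10.1. It matters because rejecting the null hypothesis is the only pass criterion (protocol 11.5), the limit is a handful of patients, and the step can remove endpoint patients but never add one.

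**Working it through.** **Inputs.** Null rate 90% and exact binomial test (protocol 7.2.1, SAP 10.4); expected rate 97%, one-sided alpha 0.025, power 90%, n = 133, 141 and 157 (protocol 11.2). Predecessor study: 90 patients inserted, 50 AEs and 2 SADEs to 3 months (protocol 5.2.4).

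**The plan's own figures.** Normal approximation: [(1.960·√(0.9·0.1) + 1.282·√(0.97·0.03)) / 0.07]² = 132.8, so 133. Exact test at n = 141: pass with at most 7 endpoint patients, alpha 0.0242, power 0.937. Power is below 90% at every n from 131 to 140. Drop-out: 133/0.9 gives 148 and 141/0.9 gives 157. All of these agree with the protocol.

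**What each reading of the note does.** Take four true endpoint patients: A has a No event and later a Yes event; B has a No and a Yes event on the same day, with the No row first in the file; C has a Yes event and later a No event; D has two Yes events on different days.

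| Step | Endpoint patients counted | Lost |
|---|---|---|
| One row per patient | 2 | A, B |
| One row per patient and onset date | 3 | B |
| Remove identical rows only | 4 | none |
| Keep Yes rows, then first row per patient | 4 | none |

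**Effect of one lost patient, starting from 8 endpoint patients in 141** (a fail, p = P(X ≤ 8 | 141, 0.10) = 0.0502):
- Patient still counted as SADE-free: 7/141, p = 0.0242, a pass.
- Patient terminated before day 77, treated as having no SADE and so removed from the denominator: 7/140, p = 0.0257, still a fail.

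**Type I error if a share q of endpoint patients is lost, true rate 90%.** The documents give no value for q.
- Denominator fixed: P(X ≤ 7 | 141, 0.10(1 − q)).
- All lost patients leave the denominator: L ~ Bin(141, 0.10q), n = 141 − L, X ~ Bin(n, 0.10(1 − q)/(1 − 0.10q)), tested at the exact limit for that n (6 for n = 127 to 140).

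| q | Denominator fixed | Lost patients leave |
|---|---|---|
| 0 | 2.4% | 2.4% |
| 5% | 3.7% | 2.6% |
| 10% | 5.5% | 3.2% |
| 16% | 8.7% | 4.7% |
| 22.5% | 13.8% | 7.6% |

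**Where 16% to 22.5% comes from.** Assume a patient-level key, a form that holds all AEs, and the same onset-time distribution for AEs and SADEs. Non-endpoint AEs per patient: λ = (50 − 2)/90 = 0.533. The chance that at least one precedes the SADE is 1 − (1 − e^(−λ))/λ = 1 − 0.413/0.533 = 0.225. Over-dispersed AE counts (gamma-mixed Poisson, shape 0.3 to 2) give 0.16 to 0.21.

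**At the design rate of 97%**, a loss of 16% to 22.5% moves the chance of passing from 93.7% to between 95.4% and 98.2%, across both treatments of the denominator.

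**The case against.** The strongest reply is that SAP 10.1 already states the rule, counts overlapping patients once, and is followed in SAP 10 by a statement that nothing further is excluded. On this view the note is shorthand for counting a patient with several endpoint SADEs once, at the first. The intent is indeed clear. But the SAP is meant to instruct the analyst, and the one step it gives for this variable does not deliver the stated quantity unless a filter is supplied from outside the note.

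The evidence for a patient-level key is not conclusive. In SAP 1.2 the patient identifier is only an example, and the table header naming it is used throughout, including over the SAP 8 table, which lists files that can hold several rows per patient. So the harmful reading is natural but not certain.

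The content of the form is also open. Protocol 7.2.1 sends SADEs to the board, and a SADE that is late or externally caused would be flagged No, so the Yes/No values do not prove that non-serious AEs are in the file. If only SADEs are there, the loss is near zero.

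Other outputs could expose a miscount: the vigilance safety report, the listings of explantations and premature terminations, and the consistency check of endpoint data in protocol 12.3. They are safeguards after the fact and do not correct the rule.

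A reader might infer that no reading of the note gives the right numerator, or that the type I error will be 14%. The documents support neither. Two readings are harmless, and the 14% needs a patient-level key, a form holding all AEs, and every lost patient staying in the denominator. The last is doubtful: protocol 8.3.5.4 terminates explanted patients, and both predecessor SADEs led to explantation.

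**Conclusion.** The point stands as a conflict between a written data step and the endpoint definition, not as proof that the analysis will be wrong. Under a patient key, or a patient-plus-date key, endpoint patients can be lost, and any loss raises the SADE-free rate. One lost patient who stays in the denominator can reverse the pass/fail result at n = 141; one who leaves it does not in the 8-of-141 case.

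The size cannot be fixed from the documents. It runs from near zero (only SADEs on the form, or a harmless key) to a type I error of about 14% at a 22% loss with the denominator held at 141. For a loss of 16% to 22% with all lost patients leaving the denominator, it is about 5% to 8%. Even an assumed 5% loss exceeds the 2.5% level under either treatment of the denominator.

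For secondary endpoint 4 there is no hypothesis, so the note affects only the 12-month estimate.

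**What to change.** In SAP 10.2, replace the note with: *keep rows with AERELPET = Yes; then sort by patient_display_id_full and AESTDT and keep the first row per patient; a patient has a primary endpoint if such a row exists, and its AESTDT is the event date for the Kaplan-Meier analysis.*

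In SAP 14.2, use the same filter-then-sort order, but with a flag that defines the 12-month SADE endpoint. AERELPET should not be copied there: SAP 10.1 sets it to Yes only when every condition of protocol 7.2.1 is met, and those conditions exclude SADEs after the 3-month follow-up.

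For 10.2 the cost is one table cell and one line of code. For 14.2 the 12-month flag must also be named or derived. The sample size (141 evaluable, 157 in total) and study conduct do not change, and the correction in 10.2 keeps the design alpha of 0.0242 at n = 141.

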## 10.1. Treatment of Missing and Spurious Data

See general definitions in chapter 5.4

## 10.2. Exclusion of Particular Information

See general definitions in chapter 5.5

No data are excluded from the analysis from the above analysis set and variables.

## 10.3. Descriptive Analyses

See general definitions in chapter 5.1 and exceptions for reporting numbers and text below the variable tables, if appropriate.

Furthermore a Kaplan-Meier analysis (including Kaplan-Meier plot) will be calculated and the estimation of the SADE-free rate (including two-sided 95% confidence interval) at 3 months (= 90 days) will be given.

## 10.4. Hypotheses & Statistical Tests

Null hypothesis:

$$H_0 : p_{SADE} \leq 90\%$$

Alternative hypothesis:

$$H_A : p_{SADE} > 90\%$$

The hypothesis will be tested by using an exact binomial test against the value of 0.9. An exact two-sided confidence interval for the SADE-free rate.

## 11. Secondary Endpoint1

*CIP chapter 7.2.2: Secondary endpoints*

### R-wave amplitude

The secondary endpoint 1 evaluates the R-wave amplitude at the 1st follow-up and at 3-month follow-up by measuring both, the lowest and the highest amplitude value via the programmer.

The secondary endpoint "R-wave amplitude" will be calculated as the mean value from the lowest and the highest amplitude.

### 11.1. Analysis set

All analyses are performed for the full analysis set.

### 11.2. Variables

| Data file, identifier patient_display_id_full | Notes | Variable name               | Variable label                        | Variable level |
|---|-------|-----------------------------|---------------------------------------|----------------|
| insertion                                     |       | DUHLRWA -> DUHLRWA_ins      | Highest amplitude value [mV]          | Scale          |
| insertion                                     |       | DULLRWA -> DULLRWA_ins      | lowest amplitude value [mV]           | Scale          |
| insertion                                     |       | DULRWA_ins_m   | mean of highest and lowest value [mV] | Scale          |
| follow_up_1st                                 |       | DUHLRWA -> DUHLRWA_fu1      | Highest amplitude value [mV]          | Scale          |
| follow_up_1st                                 |       | DULLRWA -> DULLRWA_fu1      | lowest amplitude value [mV]           | Scale          |
| follow_up_1st                                 |       | DULRWA_fu1_m   | mean of highest and lowest value [mV] | Scale          |
| follow_up_3months                             |       | DUHLRWA -> DUHLRWA_fu3      | Highest amplitude value [mV]          | Scale          |
| follow_up_3months                             |       | DULLRWA -> DULLRWA_fu3      | lowest amplitude value [mV]           | Scale          |
| follow_up_3months                             |       | DULRWA_fu3_m   | mean of highest and lowest value [mV] | Scale          |
| follow_up_12months                            |       | DUHLRWA -> DUHLRWA_fu12     | Highest amplitude value [mV]          | Scale          |
| follow_up_12months                            |       | DULLRWA -> DULLRWA_fu12     | lowest amplitude value [mV]           | Scale          |
| follow_up_12months                            |       | DULRWA_fu12_m  | mean of highest and lowest value [mV] | Scale          |

